This design avoids the confounds present in many previous studies of treatment response. First, it holds treatment intensity constant while systematically measuring the effects of varying amounts of treatment. Second, it uses both between and within-subject design components to control for a variety of potential confounding effects, including social contact, inter-subject variability, and the passage of time. Third, it examines the relationship between psycholinguistic, cognitive, and neuroanatomical factors and treatment response. Previous studies of treatment response have examined the effects of only one of these factors in accounting for differential response to treatment.

C.1 Study participants

Potential participants will be informed of the study on the PIRATE website as well as during PIRATE candidates' initial evaluation to determine eligibility for PIRATE participation. PIRATE candidates will be informed that they may be eligible to participate in the study if they meet additional study eligibility requirements. As described below, study participants will receive up to \$1500 to defray any travel expenses incurred as part of study participation, to be pro-rated if they fail to complete all study procedures (including follow-up visits).

All study participants will be community-dwelling veterans with a positive diagnosis of aphasia and the ability to live independently and carry out activities of daily living during their PIRATE program participation. Aphasia diagnosis will be provided by the referring provider, based on performance on standardized aphasia-assessment measures such as the Comprehensive Aphasia Test (CAT), the Western Aphasia Battery, Revised (WAB-R), or the Boston Diagnostic Aphasia Exam (BDAE). Aphasia diagnosis will be verified by PIRATE staff prior to enrollment based on clinical impression and performance on the CAT, with a language modality mean T-score below the 70 being required for aphasia diagnosis. Although this criterion is more liberal than the cut-off score of 62.8 described in the CAT manual, our experience suggests that patients may score above this cut-off but nevertheless present with clinically significant naming impairments. Additional exclusionary criteria for PIRATE participation are listed in Table 5 below.

Inability to carry out activities of daily living necessary for self-care
Lack of physical independence
Significant mood or behavioral disorders
Drug or alcohol dependence

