activities for participants is insufficient to explain their gains in communicative function. However, inclusion of a delayed-treatment condition will help establish this more conclusively for the current study. The specifics of the delayed-treatment condition are given in section C.2.1.

PIRATE involves a single 2-day visit to VAPHS 4-6 weeks prior to entry for a medical clearance exam and an initial comprehensive speech-language evaluation and to initiate treatment planning. During this visit, the CAT and PALPA subtests (for confirmation of aphasia diagnosis and for participant classification and treatment planning) are administered. Accepted candidates return to VAPHS at program entry and reside in residential villas at the H.J. Heinz campus of VAPHS for 4 weeks (or 5 weeks in the delayed-treatment condition). At program entry, a second CAT is administered to participants, and PIRATE candidates enrolling in the research study will be given structural MRI scans and the battery of cognitive assessments described above. Therapy is provided in existing, dedicated PIRATE treatment rooms, also located on the Heinz campus. The treatment schedule is five days a week, approximately 5 hours a day, for a total of 25 hours of therapy each week. As described below, PIRATE participants enrolled in the proposed research will receive treatment five days a week, for 4 hours per day. All therapy will be provided by PIRATE-dedicated licensed clinical providers with multiple years of experience delivering aphasia therapy. Participants return to VAPHS for a single follow-up visit 4-6 weeks after program exit.

C.2.1 Treatment:

Over 85% of PIRATE participants to date have received treatment focused on spoken word production. This is also the unit of language function and the output modality targeted in the majority of treatment-neuroanatomy/neuroimaging studies reviewed in section A.2 above, as well as the majority of treatment-cognitive prediction studies reviewed in section A.2. SFA treatment will be implemented as described by Boyle & Coelho⁸ and Boyle.⁹ At the beginning of a treatment trial, the target picture will be placed in the center of a chart containing the following entries: Group, use, action, properties, location, and association. A treatment trial will proceed through the following steps:

1. The participant is asked to name the picture.

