Treatment will be conducted five days a week (Monday through Friday) across two daily 120-minute intervals, one morning session and one afternoon session, for a total of 4 hours of treatment per day and 20 hours per week. A 20-minute break will be provided within each 120-minute treatment interval and a 120 minute break will be provided between each 120-minute treatment interval. Time in treatment will be recorded in daily logs, as will the number of exposures to each training exemplar, the number of treatment trials, and the number of features (both novel and recurring) generated for each item on a given treatment trial. In addition, participants will be engaged in planned social and recreational activities on the weekends, such as visits to

local sites and events (like a baseball game). These activities will not target or specifically stimulate language function or the skills trained in therapy.

As indicated above, half the participants will be enrolled in treatment immediately upon their arrival at VAPHS, and half will be entered into the delayed-treatment condition. Participants assigned to the delayed-treatment condition will arrive one week prior to treatment initiation. During this week, they will be in residence at the HJ Heinz campus and engage in non-language recreational activities in 2 two-hour sessions per day (the same schedule as will be followed during treatment). These activities will be led by a study staff member experienced in working with stroke survivors. The morning session will consist of recreational activities regularly conducted at the H.J. Heinz campus, listed in Table 6 below:

Billiards	Recreational Hall, H.J. Heinz campus
Physical exercise	Gym, H.J. Heinz campus
Ceramics, other visual arts	Art Studio, H.J. Heinz campus
Puzzles and board games	Recreational Hall, H.J. Heinz campus

Table 6. Non-language-focused recreational activities for participants enrolled in delayed-treatment condition

The afternoon session will consist of either complementary activities drawn from Table 6 or off-site visits to local destinations. While these sessions will afford multiple social contacts and interactions, typical of structured recreational programs, they will not target specific speech and language behaviors. Participants randomized to the delayed treatment group will receive probes (naming and PNT and other assessments [CAT, discourse measures]) on the same schedule as the no-delay group.

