The first analysis will evaluate whether the social contact associated with PIRATE participation results in improved performance on study measures, independent of any actual aphasia treatment. We will use a multivariate mixed model to test whether there are any differences between the immediate-treatment and delayed-treatment groups at the initiation of treatment, and whether there is any group-by-time interaction suggesting a positive effect of the delayed treatment week. The dependent variables will include performance on treated and untreated naming probes and PNT short forms.

If this analysis finds no significant differences between the groups, it will suggest that any observed treatment gains can be attributed to the SFA treatment rather than general effects of the social contact associated with PIRATE. In this case, the two groups will be collapsed for further analysis. In the unexpected event that this analysis finds a significant difference favoring the delayed treatment condition, it will suggest that observed treatment gains should be attributed to the combination of SFA and the socialization inherent in a residential treatment program, rather than to SFA alone. In this case, we will use the data to estimate the size of the socialization effect and statistically control for it in subsequent analyses, where possible.

C.3.1 Psycholinguistic, cognitive, and neuroanatomical predictors of treatment response

The primary dependent variable for analyses relevant to Specific Aim 1 will be the proportion of correctly-named treated stimuli at study exit (post-treatment), minus the proportion of correctly-named treated stimuli at study entry (pre-treatment). This difference score provides the simplest measure of naming treatment response. Supplementary analyses may be carried out using a related dependent variable, the percentage of possible naming improvement^[10]. This is a derived measure which divides the simple pre-post difference score

by the difference between pre-treatment naming performance and ceiling performance (100% accuracy minus observed pre-treatment accuracy). This measure helps correct for observed differences in baseline accuracy.

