Study measures will be subjected to two sets of analyses which test the dose-response hypotheses relevant to Specific Aim 2. These analyses will compare the PNT scores and acquisition and generalization probe scores across the 4 weeks of PIRATE treatment, to determine the dose-response relationship and to identify the points of largest change in response to treatment. The last of the three weekly naming probes will serve as a measure of weekly acquisition and generalization performance. This will ensure that performance on PNT and naming-probe measures may be directly compared, as they will be on the same schedule.

First, the data for the PNT scores and the acquisition/generalization probes will be analyzed with a multivariate mixed model with polynomial trend contrasts. To simplify interpretation, only time points 2 through 6 (program entry through program exit) will be included in the trend analyses. These trend analyses will first test whether there is a linear relationship between time in treatment and treatment response for study measures, as predicted by Hypothesis 2a. Second, they will test whether acquisition and generalization probes show additional curvilinear relationships to time in treatment, as predicted by Hypothesis 2b. We anticipate that there will be a positive linear trend between program entry and program exit for PNT scores and for acquisition and generalization probes. This finding would indicate that the four weeks of treatment results in significant score gains. We further predict that the trend for acquisition probes will also have a significant curvilinear (quadratic or higher-order) component, consistent with decelerating improvement across the four weeks of treatment. This finding would indicate that the largest gains for specifically treated skills/items occur early in treatment, with declining gains in later weeks. Finally, we predict that the generalization probes will also demonstrate a curvilinear relationship to time, due to accelerating improvement across the four week program. This finding would indicate that the largest gains for related but untreated items occur late in treatment, emerging later than the gains for specifically treated forms.

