Second, six pairwise planned comparisons of scores across all seven consecutive measurement intervals will be carried out, using Bonferroni-corrected t-tests to maintain the familywise type-I error rate at 0.1. As predicted by Hypothesis 2a and consistent with the preliminary outcome data from PIRATE (see B.1.3 above), we anticipate that there will be a significant increase in both PNT score and acquisition/generalization probe performance for each additional one-week increment of treatment. We also predict non-significant changes between the initial evaluation and program entry and between program exit and follow-up.

In case a linear relationship is not found between time in treatment and outcome measures, additional analyses will be carried out examining the performance of different subsets of veterans. For example, veterans will be divided into groups based on their aphasia severity, since previous treatment findings have suggested that milder aphasia severity may be associated with less change on language-performance measures^[1]. Separate trend analyses will be carried out for the different severity groups, to examine whether different dose-response relationships may be observed for different aphasia groups.

In addition to these within-participant analyses examining dose-response relationships, a complementary set of between-participants analyses will be carried out, examining the effects of two versus four weeks of treatment for different randomly-selected groups of participants. It is standard practice in the dose-response literature to compare the response of groups exposed to different amounts of a therapeutic

agent, to see the incidence of positive or negative responses to the agent in the groups (e.g., frequency of remission or toxicity^[110]). These complementary between-participant analyses will simulate this comparison for the current study, providing an additional randomized-control measure of the effect of high dosage SFA on individuals with naming impairments. For these analyses, participants will be randomized to one of two groups. For half the participants, outcome measures (naming and PNT scores) will be sampled after two weeks' exposure, while for the other half, outcome measures will be sampled after the full four weeks of treatment. We anticipate that changes in study measures will be larger for the four-week group than for the two-week group.

C.3.3 Additional analyses of general language performance and connected speech

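### The Aim 2 linear-trend, weekly-increment and two- versus four-week analyses cannot separate weeks of SFA from elapsed time; time is controlled only indirectly, and the randomised one-week offset is not used for the dose question

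*Combined protocol and SAP*

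**What the plan says.** Section C lists as an advantage that the design's between- and within-subject components serve "to control for a variety of potential confounding effects, including social contact, inter-subject variability, and the passage of time".

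The dose analyses are in C.3.2. The trend model tests "whether there is a linear relationship between time in treatment and treatment response for study measures", and "only time points 2 through 6 (program entry through program exit) will be included in the trend analyses". Paired comparisons of consecutive measurements follow, across all seven points. Two of those intervals are untreated: "We also predict non-significant changes between the initial evaluation and program entry and between program exit and follow-up". In a further comparison, for a random half of participants "outcome measures (naming and PNT scores) will be sampled after two weeks' exposure", and for the other half after four weeks; everyone is scheduled for the full four weeks.

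Half the participants are randomised to a one-week residential delay (C.2, C.2.1) and are tested "on the same schedule as the no-delay group". C.3 uses this randomisation to test for a social-contact effect. If no significant difference appears, "the two groups will be collapsed for further analysis". If the delayed arm does better, the effect is to be estimated and controlled for where possible.

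**The concern.** Hypothesis 2a asks what each additional week of SFA adds. If naming drifts upward for another reason, such as repeated probing, residence or familiarity with testing, a model in which treatment weeks and elapsed weeks coincide attributes that drift to dose.

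The exposure is greatest for the naming probes. C.2.2 builds seven PNT forms so that PNT gains cannot come from seeing the same pictures again. The 120 probe items have no such protection: the same items are shown three times a week, and gains on the untreated ones are read as generalisation.

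The trial already contains randomised information on this. At the same residential week the immediate arm has had one more week of SFA than the delayed arm. C.3.2 does not use it.

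**Working it through.** **1. Are dose and time separable?** The plan gives no power or sample-size calculation for Aim 2 to reproduce, so this is a structural check.
- Trend model, time points 2 to 6: dose = 0, 1, 2, 3, 4 and elapsed week = 0, 1, 2, 3, 4. The correlation is 1.00, and the matrix [1, dose, time] has rank 2 of 3.
- With drift g per week and no SFA effect, the linear slope is biased by g. The two- versus four-week difference is biased by 4g − 2g = 2g, because only the sampling time is randomised. The quadratic contrast (2, −1, −2, −1, 2) of a linear drift is 0.
- All seven points, with untreated gaps of 4 to 6 weeks on each side (C.2): the correlation falls to 0.84–0.88 and the rank is 3 of 3. A constant drift could be estimated, but C.3.2 only tests these gaps for change.
- Both arms aligned by residential week: the immediate arm has w weeks of SFA and the delayed arm w − 1. Drift bias in the contrast is gw − gw = 0. A model with free week and free dose effects has full rank (10 of 10 columns).

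**2. How large might drift be?** B.1.2 reports F and MSE for the pilot PICA z-scores. Mean change = √(F × MSE / n).

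| Analysis | Untreated interval | Treatment interval |
|---|---|---|
| Complete cases, n = 35 | √(2.574 × 0.009 / 35) = 0.026 | √(56.364 × 0.010 / 35) = 0.127 |
| Mean-imputed, n = 41 | √(6.042 × 0.014 / 41) = 0.045 | √(53.168 × 0.013 / 41) = 0.130 |

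This reads MSE as that of the raw difference. B.1.3 supports the reading. There 0.035 is about 33% of the three-week change and 25% of the four-week change, giving 0.106 and 0.140; weighted by 15 and 27 participants this is 0.128.

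Over 4 to 6 untreated weeks, drift is 0.026/6 = 0.004 to 0.045/4 = 0.011 z per week. Table 1 gives a percentile-rank SD of 15 about the 51st percentile, which is roughly 0.38 z. Dividing by 0.38 gives about 0.011 to 0.030 SD per week. This rescaling, and carrying it from PICA to naming, are assumptions.

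**3. Effect on the planned trend.** Assumptions: PNT in SD units, true-score variance 0.87 and error variance 0.13 (from the inter-form correlation of 0.87 in C.2.2), between-person slope SD 0.05, and 50 participants.

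SE of the mean slope = √[(0.13/10 + 0.05²)/50] = √(0.0155/50) = 0.0176.

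| Drift, SD per week (no SFA effect) | Drift / SE | Trend significant at two-sided 0.05 |
|---|---|---|
| 0 | 0 | 5% |
| 0.011 | 0.62 | 9% |
| 0.017 | 0.97 | 16% |
| 0.030 | 1.70 | 39% |

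Simulation agrees (9%, 16% and 38% for the last three rows). The offset contrast stays at about 5% throughout.

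**4. Precision of the offset contrast.** Take the mean of residential weeks 1 to 4, adjusted for the arrival score, with 25 per arm.
- Residual variance = 0.87 + 0.05² × 2.5² + 0.13/4 − 0.87² = 0.161.
- SE = √(0.161 × 2/25) = 0.114 SD.
- Power is 0.58 for a gain of 0.25 SD per week and 0.86 for 0.35; neither gain comes from the documents.
- At the pilot's extra-week value (0.035 z; 0.035/0.38 = 0.09 SD) power is about 0.12.
- A single unadjusted weekly contrast, 25 v 25, has power 0.26 at the pilot d of 0.37 printed in B.1.3, and 80% power only for 0.79 SD.

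**The case against.** The best defence is that the sentence in section C describes the design, not the trend model, and that the design does contain controls for time. Two untreated intervals sit inside Aim 2. Nonword repetition is probed weekly as a within-subject control. Seven equated PNT forms limit exposure effects on that outcome. Enrolment beyond six months post-onset limits spontaneous recovery. The randomised delay is tested by group and by group-by-time. This stands: a reader might infer that control for time is absent, and the documents do not support that. It is indirect. The untreated intervals contain no intensive probing, C.3 assigns no analysis to nonword repetition, and the delay test covers one week.

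Other parts also stand:
- Pooling is conditional on a non-significant test.
- Equal numbers of tests at each residential week cannot be assumed. C.2.1 does not say whether the shared schedule runs from arrival or from treatment start, and C.2.2 ties the first probe to treatment initiation. With seven PNT forms, a delayed participant tested at both arrival and treatment start could need an eighth administration.
- A drift of 0.05 SD per week would make the trend significant in 79% of null trials, but it exceeds the pilot-implied range.
- The upper pilot figure comes from an imputation that B.1.2 says probably overstates baseline change; the complete-case change was non-significant (p = 0.118).
- The offset contrast has low power at pilot-sized gains.

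None of this separates dose from time in the C.3.2 linear analyses.

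**Conclusion.** The concern holds in limited form. The linear trend, the weekly increments and the two- versus four-week comparison cannot distinguish SFA weeks from elapsed time and repeated testing, and the indirect safeguards do not enter the dose model. That collinearity follows from the schedule and needs no assumption.

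The size does need assumptions. At drift of about 0.01 to 0.03 SD per week, a null pooled trend would be significant in roughly 10% to 40% of trials, against 5% for the offset contrast. This rests on the PICA back-calculation, the 0.38 z rescaling and the variance values above.

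Two stronger readings should be avoided. Hypothesis 2b is not undermined in the same way: curvature is exposed only to non-linear drift. Nor would the offset settle the dose-response question alone: it is free of drift common to both arms, but imprecise. The change is worth making because it is cheap and uses randomisation already in place.

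**What to change.** - **C.3.2:** add a supplementary joint model that keeps both arms, indexed by weeks since arrival. Include residential week as a categorical term, SFA weeks received as the dose term, and the pre-treatment score as covariate: the arrival score if both arms are tested at arrival, otherwise the initial-evaluation score. Report the average between-arm difference with a confidence interval as the time-controlled value of one additional week, beside the planned within-person trend.
- **C.2.1:** state whether the delayed arm's test schedule runs from arrival or from treatment start. The 2-v-1, 3-v-2 and 4-v-3 contrasts need only the weekly in-treatment probes. The 1-v-0 contrast and equal test counts need testing anchored to arrival.
- **Section C:** describe control for the passage of time in the trend analyses as indirect.

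Cost: some wording and one extra model on data that are largely already planned. If testing is not anchored to arrival, 1-v-0 is unavailable unless a test is added. The main drawback is imprecision (SE about 0.11 SD under the assumed variances), so the result should be presented as an estimate alongside the trend, not as a replacement or a pass/fail test.
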